# **Secondary Objective**

- To describe the typical diabetes treatment regimes in women with diabetes of reproductive age.
- To determine the overall diabetes control in women with diabetes of reproductive age.
- To examine the number of women of reproductive age who have diabetes-related complications.

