# 3. STUDY DESIGN

Non-interventional, cross-sectional questionnaire study in women of child-bearing age 1 hours per participant, 6 months total n=100 participants total

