# 4.2 Exclusion Criteria

- Inability to understand and write in the English language
- Unable to participate due to other factors, as assessed by the Chief Investigators
- A history of gestational diabetes but not diabetes mellitus.
- Pregnant women

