# 7. STATISTICS AND DATA ANALYSIS

Approximately 100 potential participants will be identified from the list of persons who attend the Imperial College Healthcare NHS Trust diabetes clinics. This is based on the known total number of people who attend these clinics (approximately 2000), assuming that 50% will be women and 50% of these will be of reproductive age. All potential participants will be sent the study pack. A response rate of 10-20% is assumed following previous questionnaire studies undertaken at Imperial College of patient populations.

This study contains both descriptive and quantifiable data. The quantitative outcomes may be either ordinal or categorical, and proportions tests, including Chi squared tests, t-tests and ANOVAs will be used to determine differences between these outcomes.

The descriptive data will be tabulated and presented as such without statistical analysis.

All personal details will be sent via encrypted email (nhs.net).

Record linking participant information to study ID will be stored securely on an Imperial College NHS trust Computer. All study data will be stored in a pseudonymised format in an encrypted database on an Imperial College NHS trust computer.

Direct quotations may be published in anonymous fashion. Care will be taken to ensure no other incidental details (such as ethnicity or age) will be associated with the quotation, in order to ensure anonymity. The NHS Code of Confidentiality will be followed at all times. All data is to be stored in a pseudonymised form by using study codes for de-identification of participants. Examples of such a code includes: CAPRE-DM 0001 (assigned in order of enrolment). Identifiable Personal data will be kept in files in a locked office within Imperial College Healthcare NHS Trust, accessible only by the research/clinical team. Pseudonymised data will be stored in a password encrypted spreadsheet on ICHT computers, accessible only by the research team.

Data and all appropriate documentation will be pseudonymised and stored for a minimum of 10 years after the completion of the study in line with Imperial College policy.

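### Section 7's figure of about 100 potential participants does not follow from its own inputs, which give about 500 women invited and 50 to 100 responders; the secondary results should be worded as applying to responders

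*Combined protocol and SAP*

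**What the plan says.** Section 7 (Statistics and Data Analysis) opens: "Approximately 100 potential participants will be identified from the list of persons who attend the Imperial College Healthcare NHS Trust diabetes clinics". It derives this from roughly 2000 people attending the clinics, "assuming that 50% will be women and 50% of these will be of reproductive age". It continues, "All potential participants will be sent the study pack", and then, "A response rate of 10-20% is assumed following previous questionnaire studies undertaken at Imperial College of patient populations".

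The Study Summary gives the population as n=100, and section 3 (Study Design) gives "n=100 participants total". The exclusion criteria in section 4.2 reduce the list further, for example through "Inability to understand and write in the English language", and also through pregnancy and investigator judgement.

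The secondary objectives in section 2 include "To describe the typical diabetes treatment regimes in women with diabetes of reproductive age" and "To determine the overall diabetes control in women with diabetes of reproductive age"; a third concerns how many women have complications. Section 6 limits record review to women who have consented, and limits the analysis to returned questionnaires. Section 3.1 lists treatment, complications and HbA1c as baseline data on participants, and section 10 summarises clinical data for the study population. No section plans to report how many women were invited or what response was achieved.

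**The concern.** Two things are at issue.

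The first is a count that fails on its own terms. One paragraph gives a number of women to be approached, the inputs for that number, and a response rate to apply to it, but the inputs do not produce the number. The number invited is the denominator of the response rate, and it determines whether the planned total can be reached. With no power or precision calculation in the plan, this paragraph is the only justification for the study's size.

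The second is whom the secondary results describe. The objectives refer to women with diabetes of reproductive age in general. The data will come from those who reply and consent, which on the plan's own rate is 10 to 20% of those invited. Section 1.2 says the findings will be used to develop services, so a reader needs to know which women the figures represent.

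**Working it through.** **Inputs, all from section 7 unless stated.** Attenders: about 2000. Share women: 50%. Share of those of reproductive age: 50%. Response: 10 to 20%. Planned total: 100 (Study Summary and section 3).

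**Step 1: try to reproduce the stated figure.** Potential participants = 2000 × 0.50 × 0.50 = 500. The stated figure is about 100, so it does not reproduce; the inputs give five times as many.

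**Step 2: apply the response rate.** 500 × 0.10 = 50 and 500 × 0.20 = 100. The figure of 100 does appear here, as the number of responders at the upper limit.

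**Step 3: invitations needed for 100 responders.** 100 / 0.20 = 500, the whole pool. 100 / 0.10 = 1000, twice the pool.

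**Step 4: allow for exclusions.** The documents do not say how many women the exclusions remove, so these pool sizes are assumptions.

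| Women left | Responders at 10–20% | Response needed for 100 |
|---|---|---|
| 500 | 50–100 | 100/500 = 20% |
| 450 (assumed) | 45–90 | 100/450 = 22.2% |
| 400 (assumed) | 40–80 | 100/400 = 25% |

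Any loss to exclusions puts 100 above the assumed range.

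**Step 5: what 50 rather than 100 means for precision.** The 95% half-width for a proportion is 1.96 × √(p(1−p)/n). At p = 50%, chosen because it gives the widest interval, it is 13.9 points for n=50 and 9.8 points for n=100, without a finite-population correction.

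**Step 6: self-selection, illustration only.** For response rate r and a difference d between responders and non-responders, the responder figure differs from the invited-list figure by (1 − r) × d. The documents give no value for d. For assumed differences of 5, 10 and 20 points, the result is 4, 8 and 16 points at r = 20%, and 4.5, 9 and 18 points at r = 10%. An interval calculated from responders alone would not show this component.

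**The case against.** The strongest reply on the count is that it is a slip of wording. 500 × 20% is exactly 100, and both the Study Summary and section 3 give 100 as the study total, so 100 was probably meant as the number of responders. That reading is the likely one. It does not rescue the sentence, which calls the 100 potential participants and sends all of them the pack, and it takes the top of the range as the plan.

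A reader might infer something stronger: that only 100 women will be invited, so only 10 to 20 will reply. The documents do not support that as a measure of impact, because it conflicts with n=100 in two other places and with the inputs beside it.

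It can also be said that the 10 to 20% may not apply to women approached face to face in clinic (section 6, route c), so a total of 100 may be more attainable than the arithmetic suggests. This stands as an open question, because section 7 does not say which routes the rate covers.

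On the secondary objectives, sections 3.1 and 10 already label the clinical data as belonging to participants or to the study population, and the study is descriptive. That reduces the point to one of wording and reporting, but the objectives remain broader than the data. A reader might also infer that the results will be biased. Nothing in the documents shows this; the differences in step 6 are assumed.

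**Conclusion.** The count in section 7 is wrong as written. On the plan's own inputs, about 500 women would be invited before exclusions and about 50 to 100 would respond. The planned 100 is the upper limit of that range, not its centre, and falls outside it once any women are excluded. This rests only on the stated inputs and on the 10 to 20% applying to every contact route.

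The second part is real but smaller. The secondary objectives are worded for a wider group than the consenting responders who supply the record data, and the plan reports neither the number invited nor the response achieved. The size and direction of any self-selection are unknown, and no bias has been demonstrated. The questionnaires and the data flow figure were not available to check.

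**What to change.** **Count (text only).** Restate the opening of section 7 along these lines: about 500 women of reproductive age are expected on the clinic list before exclusions; all who are eligible will be invited; at a response of 10 to 20%, about 50 to 100 responders are expected. Make the Study Summary and section 3 agree, for example by giving the total as up to 100. State whether the 10 to 20% includes women approached in clinic under route (c) of section 6.

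**Reporting (text only).** Add to section 7 that the number of women invited and the response rate achieved will be reported, and that the results on treatment, diabetes control and complications will be described as applying to responders at this Trust's clinics.

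**Optional.** If approvals and the available fields allow, the direct-care team could supply anonymised aggregate counts for all invited women, to be shown beside the responder figures. This may need an approvals amendment, because section 6 limits record review to consenters and the documents do not say which fields the list holds. To be useful, the counts should cover the secondary objectives: age band and diabetes type alone would not, whereas an HbA1c band would address diabetes control. Such a table cannot show differences in knowledge, the primary objective. If it is not feasible, the text changes suffice.

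The text changes need no additional participants, visits or data from participants.

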# 2. STUDY OBJECTIVES

# **Primary Objective**

- To establish what knowledge women of childbearing age with diabetes have of
  - o The risks and management of diabetes in pregnancy
  - o The effect of diabetes on fertility
  - o What forms of contraception women with diabetes use

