# 3.1 Study Outcome Measures

- Quantitative data:
- Number of women planning a pregnancy within the next year
- Invitation to and attendance at pre-conception counselling
- Current contraceptive choices
- Knowledge of effect of diabetes on fertility
- Number of women who have had the importance of a planned pregnancy explained to them
- 2. Descriptive data
- Women's knowledge of the risks to the mother during pregnancy if the mother has diabetes
- Women's knowledge of the risks to the fetus during pregnancy if the mother has diabetes

Additional baseline participant data:

- Age
- Ethnicity
- · Number of previous pregnancies
- Type of diabetes
- · Length of diabetes
- Current diabetes treatment
- Diabetes complications: nephropathy, neuropathy, retinopathy, cardiovascular disease
- Recent HbA1C
- Other medical conditions
- Other medications

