Within the patient information sheet there will be contact details for the research team, should the participant wish to discuss the study and obtain any further details.

Once returned, the pseudonymised questionnaire data will be recorded in a password encrypted database on an Imperial College Healthcare NHS Trust computer (subsequently known as the results database). Informed consent will be filed in the trial master file. Data from Qualtrics will be downloaded in a PDF format on either an ICL or ICHT computer and printed for hard copy records. Questionnaire scoring data will be pulled from Qualtrics in a

pseudonymised format and saved on either an ICL or ICHT computer within an encrypted, password protected document.

Once informed consent has been provided, The research team will then review the electronic health records of those participants who have consented to record biochemical data, medical history and baseline demographics. This data will be recorded in pseudonymised form in the results database.

In all cases, no samples are taken and all data will be pseudonymised. No follow up outside of usual care will be provided.

End of study will be defined as last subject last visit (LSLV).

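### Section 7 assigns tests of means to outcomes it calls ordinal or categorical, and plans no confidence interval for the proportions that answer the descriptive objectives

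*Combined protocol and SAP*

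**What the plan says.** The design in section 3 is a "Non-interventional, cross-sectional questionnaire study in women of child-bearing age", with no arms. The objectives in section 2 are descriptive. The primary objective covers knowledge of risks and management, knowledge of the effect on fertility, and "What forms of contraception women with diabetes use". A secondary objective is "To examine the number of women of reproductive age who have diabetes-related complications".

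Section 3.1 lists five quantitative outcomes, among them "Current contraceptive choices". It places knowledge of risks to mother and fetus under descriptive data. Age, length of diabetes, HbA1c and complications are listed as baseline data.

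Section 7 states the scale of the outcomes: "The quantitative outcomes may be either ordinal or categorical". The same sentence gives the method: "proportions tests, including Chi squared tests, t-tests and ANOVAs will be used to determine differences between these outcomes". The descriptive data are to be tabulated and not tested. Section 10 adds that anthropometry and personal clinical data will be summarised by mean or median and spread. No confidence interval is planned anywhere in the document.

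**The concern.** There are two linked difficulties.

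- **Scale.** T-tests and ANOVA compare means, yet the sentence ties them to outcomes it has just called ordinal or categorical. For unordered categories such as contraceptive methods, a mean depends on how the categories happen to be numbered and says nothing about the women.
- **Question.** No objective asks whether one thing differs from another. The objectives ask what women know, what they use and how many have complications. The natural answer is a proportion with its denominator and its precision. The plan offers tests of difference instead and gives no measure of precision.

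Section 1.2 says the data will be used to develop services and pre-conception counselling. A reader of the results should be able to see how far a reported percentage could move through sampling error alone.

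**Working it through.** **Step 1. Set the outcomes beside the tests.** The item formats are not in the document, so this uses the outcomes as section 3.1 names them.

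| Outcome | Natural form | Does a test of means suit it? |
|---|---|---|
| Planning a pregnancy; invitation to and attendance at counselling; importance of planning explained | Count of women, hence a proportion | Not the natural choice; a proportion or chi-squared is |
| Contraceptive choice | Unordered categories | No |
| Knowledge of the effect on fertility | Categorical, ordinal or scored | Only if there is a numeric score |

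The variables that clearly suit a t-test or ANOVA (HbA1c, age, length of diabetes) are baseline data in section 3.1. Section 7 does not direct these tests to them.

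**Step 2. Reproduce the expected number of returns.** Section 7 gives about 2000 clinic attenders, 50% women, 50% of these of reproductive age, and says: "A response rate of 10-20% is assumed following previous questionnaire studies".

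- Eligible women: 2000 × 0.50 × 0.50 = 500
- Returns at 10%: 500 × 0.10 = 50
- Returns at 20%: 500 × 0.20 = 100

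The planned n = 100 in section 3 is therefore reached only at the top of the assumed range. Section 7 also describes about 100 potential participants, which does not match the 500 from its own inputs. That is a separate matter. Taken literally it would leave fewer returns and wider intervals.

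**Step 3. Precision of a proportion.** The Wilson 95% interval, with z = 1.96, is

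[p + z²/(2n) ± z√(p(1−p)/n + z²/(4n²))] / (1 + z²/n)

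For p = 0.35, the share in section 1.1 who recalled any discussion of pregnancy in an earlier survey, used here only as an illustration:

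- n = 50: (0.35 + 0.0384 ± 1.96 × 0.0702) / 1.0768 = 0.361 ± 0.128, or 23.3% to 48.9%
- n = 100: (0.35 + 0.0192 ± 1.96 × 0.0487) / 1.0384 = 0.356 ± 0.092, or 26.4% to 44.7%

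Exactly 35% cannot be observed in 50 women. The nearby 18/50 (36%) gives 24.1% to 49.9%. Other illustrative values:

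| Observed | n = 50 | n = 100 |
|---|---|---|
| 10% | 4–21% | 6–17% |
| 20% | 11–33% | 13–29% |
| 35% | 23–49% | 26–45% |
| 50% | 37–63% | 40–60% |

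**Step 4. Would a finite-population view remove the problem?** Suppose inference is limited to the 500 eligible women. Replace n by n × 499/(500 − n):

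- n = 50: 50 × 499/450 = 55.4, interval 24–48%
- n = 100: 100 × 499/400 = 124.75, interval 27–44%

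The imprecision remains.

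**The case against.** The strongest reply is that the sentence is only a loose list: proportions tests for categorical items, and t-tests and ANOVA for whatever is continuous. It could even mean comparing HbA1c or age across categories of an outcome, where t-tests and ANOVA are standard. Section 6 says "Questionnaire scoring data will be pulled from Qualtrics", so a numeric score may exist, and the questionnaires (Appendix 1) are attached separately. Chi-squared is already listed and is sound for categorical data. Tests of means are also close to calibrated on binary or ordinal items.

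Much of this stands, and it is why the point is minor. What it does not remove is that section 7 applies the tests to outcomes described as ordinal or categorical and never assigns tests of means elsewhere.

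A second reply is that a missing interval is a matter of reporting, since a reader given n/N can work one out, and that non-response at 10–20% is probably the larger uncertainty. The first part is fair but is no reason to leave the interval out of a descriptive study. The second is true: an interval shows sampling error only. It would not correct for non-response, nor on its own settle a comparison with an earlier survey.

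Three stronger readings are tempting and are not supported:

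- A reader might infer that means of contraceptive codes will be calculated. The document does not say so.
- A reader might infer a multiplicity problem by crossing every outcome with every baseline variable. The document does not say how many comparisons will be run, so no false-positive rate can be attached to this study.
- A reader might treat the absence of named comparison groups as a flaw in its own right. In a descriptive survey it is missing detail that calls for clarification.

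**Conclusion.** The point holds as a minor one. As written, section 7 assigns tests of means to outcomes it calls ordinal or categorical, which is the wrong method for a nominal outcome such as contraceptive choice. It makes tests of difference the only stated analysis of the quantitative outcomes, although the objectives are descriptive. The mean or median and spread promised in section 10 concern clinical data and do not give the precision of a proportion.

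The omitted uncertainty is material: for an observed 35%, about 13 percentage points either way at 50 returns and about 9 at 100. These figures assume that the 500 eligible women are approached and that 10–20% respond, as section 7 implies. They treat respondents as a simple random sample, which makes them a lower bound on the real uncertainty. The observed proportions are illustrative. The scale mismatch is judged from the outcome names, because the item formats could not be seen.

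**What to change.** Replace the testing sentence in section 7 with:

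> The main analysis of each quantitative outcome, of each diabetes complication, and of any risk-knowledge item that is coded as known/not known, is n/N and the proportion (or category distribution) with a 95% Wilson confidence interval. Any subgroup comparison is exploratory: categorical outcomes by chi-squared or Fisher's exact test, ordinal outcomes by a rank-based test, and t-tests or ANOVA only for continuous variables (e.g. HbA1c, age, length of diabetes) or a defined numeric score.

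Complications and coded risk-knowledge items are named because the objectives cover them but section 3.1 does not list them as quantitative outcomes. Free-text risk-knowledge answers stay tabulated without testing, as planned. As a clarification, list any subgroups to be compared, or state that there are none.

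The cost is one rewritten paragraph and slightly more analysis work. It requires no new data, participants or visits.

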# 8. REGULATORY ISSUES

### 8.1 Ethics approval

The Study Coordination Centre has obtained approval from the xxx Research Ethics Committee (REC) and Health Regulator Authority (HRA). The study must also receive confirmation of capacity and capability from each participating NHS Trust before accepting participants into the study or any research activity is carried out. The study will be conducted in accordance with the recommendations for physicians involved in research on human subjects adopted by the 18th World Medical Assembly, Helsinki 1964 and later revisions.

#### 8.2 Consent

Consent to enter the study must be sought from each participant only after a full explanation has been given, an information leaflet offered and time allowed for consideration. Signed participant consent should be obtained. The right of the participant to refuse to participate without giving reasons must be respected. After the participant has entered the study the clinician remains free to give alternative treatment to that specified in the protocol at any stage if he/she feels it is in the participant's best interest, but the reasons for doing so should be recorded. In these cases the participants remain within the study for the purposes of follow-up and data analysis. All participants are free to withdraw at any time from the protocol treatment without giving reasons and without prejudicing further treatment.

# 8.3 Confidentiality

Anonymised quotes may be used in publications if the participant has given written informed consent. The Chief Investigator will preserve the confidentiality of participants taking part in the study and is registered under the Data Protection Act.

# 8.4 Indemnity

Imperial College London holds negligent harm and non-negligent harm insurance policies which apply to this study.

# 8.5 Sponsor

Imperial College London will act as the main Sponsor for this study. Delegated responsibilities will be assigned to the NHS trusts taking part in this study.

